10.0 CRITERIA FOR RESPONSE

The primary endpoint is the overall response rate (ORR) per IWG-2006 criteria¹³. This is summarized in table 9 and 10. Response will include complete remission, partial remission, marrow complete remission and any hematological improvement achieved any time during the duration of the therapy.

Table 9. Proposed modified International Working Group response criteria for altering natural history of MDS⁷

Category	Response criteria (responses must last at least 4 wk)
Complete remission	Bone marrow: ≤5% myeloblasts with normal maturation of all cell lines

	
Persistent dysplasia will be noted[†]
 
Peripheral blood[‡]
 
 • Hgb ≥ 11 g/dL • Platelets $\geq 100 \times 10^9/L$ • Neutrophils $\geq 1.0 \times 10^9/L$[†] • Blasts 0%
Partial remission	
All CR criteria if abnormal before treatment except:
 
 • Bone marrow blasts decreased by $\geq 50\%$ over pretreatment but still $> 5\%$ • Cellularity and morphology not relevant
Marrow CR [†]	
Bone marrow: $\leq 5\%$ myeloblasts and decrease by $\geq 50\%$ over pretreatment[†]
 
Peripheral blood: if HI responses, they will be noted in addition to marrow CR[†]

Stable disease	
Failure to achieve at least PR, but no evidence of progression for > 8 wks

Failure	
Death during treatment or disease progression characterized by worsening of cytopenias, increase in percentage of bone marrow blasts, or progression to a more advanced MDS FAB subtype than pretreatment

Relapse after CR or PR	
At least 1 of the following:
 
 • Return to pretreatment bone marrow blast percentage • Decrement of $\geq 50\%$ from maximum remission/response levels in granulocytes or platelets • Reduction in Hgb concentration by ≥ 1.5 g/dL or transfusion dependence
Cytogenetic response	
Complete
 
 • Disappearance of the chromosomal abnormality without appearance of new ones 
Partial
 
 • At least 50% reduction of the chromosomal abnormality

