Disease progression	
For patients with:
 
 • Less than 5% blasts: $\geq 50\%$ increase in blasts to $> 5\%$ blasts • 5%-10% blasts: $\geq 50\%$ increase to $> 10\%$ blasts • 10%-20% blasts: $\geq 50\%$ increase to $> 20\%$ blasts • 20%-30% blasts: $\geq 50\%$ increase to $> 30\%$ blasts 
Any of the following:
 
 • At least 50% decrement from maximum remission/response in granulocytes or platelets • Reduction in Hgb by ≥ 2 g/dL • Transfusion dependence
Survival	
Endpoints:
 
 • Overall: death from any cause • Event free: failure or death from any cause • PFS: disease progression or death from MDS • DFS: time to relapse

- Cause-specific death: death related to MDS

Table 10. Proposed modified International Working Group response criteria for hematologic improvement⁷

Hematologic improvement [*]	Response criteria (responses must last at least 8 wk) [†]
Erythroid response (pretreatment, < 11 g/dL)	Hgb increase by ≥ 1.5 g/dL Relevant reduction of units of RBC transfusions by an absolute number of at least 4 RBC transfusions/8 wk compared with the pretreatment transfusion number in the previous 8 wk. Only RBC transfusions given for a Hgb of ≤ 9.0 g/dL pretreatment will count in the RBC transfusion response evaluation [†]
Platelet response (pretreatment, < $100 \times 10^9/L$)	Absolute increase of $\geq 30 \times 10^9/L$ for patients starting with $> 20 \times 10^9/L$ platelets Increase from $< 20 \times 10^9/L$ to $> 20 \times 10^9/L$ and by at least 100% [†]
Neutrophil response (pretreatment, < $1.0 \times 10^9/L$)	At least 100% increase and an absolute increase $> 0.5 \times 10^9/L$ [†]
Progression or relapse after HI [‡]	At least 1 of the following: At least 50% decrement from maximum response levels in granulocytes or platelets Reduction in Hgb by ≥ 1.5 g/dL Transfusion dependence

Secondary endpoints include:

1. To evaluate efficacy of Pacritinib based on the presence of JAK2 and FLT3 mutations at diagnosis.
2. To evaluate efficacy based on IPSS, R-IPSS and LR-MDS risk classification systems at diagnosis.

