12.0 STATISTICAL CONSIDERATIONS

General Description

This is a Phase II open-label study designed to evaluate the efficacy and toxicity of Pacritinib as single agent (Part 1) and Pacritinib + HMA (Part 2) in subjects with lower-risk myelodysplastic syndrome. The primary efficacy outcome of both parts is the overall response rate (ORR) based mainly on hematologic improvement defined by IWG-2006 criteria, and which also includes complete remission (CR), partial remission (PR) and marrow complete remission. In Part 1, patient's overall response will be assessed after 1 cycle of treatment but no more than after 4 cycles of treatment; cycle length is 28 days. If no response is attained after 4 cycles of treatment or if progression occurs during therapy at any time, the patient is eligible to continue on Pacritinib + HMA (Part 2). Part 2 will not continue if Part 1 is stopped early. A maximum of 40 total evaluable patients (n=40) will be enrolled.

Study design: Part 1

The standard practice is to put these patients on observation, an ORR rate of about 15% is clinically relevant. The target ORR with the experimental treatment is 15%. The regimen of the Pacritinib will be considered worthy of further investigation if it elicits an increase in ORR to 15% with acceptable toxicity. A >15% therapy related non-hematological grade 3/4 toxicity rate is considered unacceptable. Thus, interim monitoring rules, assuming the prior distributions below, were constructed that meet the following two conditions,

- 1) Stop if $\text{Prob}\{p(\text{ORR}, E) < 0.15 \mid \text{data}\} > 0.975$, or
- 2) Stop if $\text{Prob}\{p(\text{TOX}, E) > 0.15 \mid \text{data}\} > 0.975$,

where $P(\text{ORR}, E)$ and $P(\text{TOX}, E)$ are the true ORR and toxicity rates for the Pacritinib, and $p(\text{ORR}, H)$ is the true ORR rate of the standard treatment. The first rule provides for stopping the study if the data suggest that it is unlikely (i.e., probability < 2.5%) that ORR rate of the Pacritinib treatment is greater than 15.0%. The second condition will stop the study early if excessive therapy-related non-hematological grade 3/4 toxicity (>15%) is highly probable (i.e., probability >97.5%) for the Pacritinib. Monitoring for toxicity and futility will not begin until 5 patients have been evaluated, and cohort size for future evaluations is 5.

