All patients who received any dose of the study agent will be included in the analysis for efficacy and safety. Demographic/clinical characteristics (i.e. including duration of response) and safety data of the patients will be summarized using descriptive statistics such as mean, standard deviation, median and range. For the primary efficacy analysis, we will estimate the ORR for the Pacritinib and Pacritinib + HMA, along with the 95% confidence interval. Patients who drop out of the study before completing all the cycles will be treated as “failures” for the primary analysis. Overall response rate (ORR) during the study period will also be presented with the 95% confidence interval. The association between ORR and patient’s clinical characteristics will be examined by Wilcoxon’s rank sum test or Fisher’s exact test, as appropriate. Toxicity type, severity and attribution will be summarized for each patient using frequency tables. The distribution of time-to-event endpoints (EFS and OS) including overall survival and event free survival will be estimated using the method of Kaplan and Meier. Comparisons of time-to-event endpoints by important subgroups will be made using the log-rank tests. The additional treatment in part 2 will be included in time-to-event analysis as time-dependent covariates.

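### The EFS/OS analysis calls for Part 2 treatment as a time-dependent covariate but names no model that takes one, and the coefficient would not measure the effect of adding HMA

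*Combined protocol and SAP*

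**What the plan says.** The Statistical Analysis Plan part of Section 12.0 says that EFS and OS "will be estimated using the method of Kaplan and Meier". It continues: "Comparisons of time-to-event endpoints by important subgroups will be made using the log-rank tests". The next sentence is: "The additional treatment in part 2 will be included in time-to-event analysis as time-dependent covariates". It names no regression model, time origin, censoring rule or adjustment variables, and it does not define the EFS event.

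The definition has to come from Table 9 in Section 10.0: "Event free: failure or death from any cause". The same table describes failure as "Death during treatment or disease progression characterized by worsening of cytopenias", a rise in marrow blasts, or a move to a more advanced subtype. Stable disease is a separate row: no PR or better, "but no evidence of progression for > 8 wks".

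The General Description in Section 12.0 gives the routes into Part 2: "If no response is attained after 4 cycles of treatment or if progression occurs during therapy at any time". Section 4.0 equates non-response with stable disease and keeps responders on pacritinib alone. Enrolment is capped at 40 evaluable patients.

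**The concern.** There are three difficulties.

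- **Missing model.** A Kaplan-Meier curve and a standard log-rank test have no place for a covariate that changes during follow-up. Extended Cox, Mantel-Byar and Simon-Makuch methods exist, but the plan names none, so two analysts could produce different results from the same text.
- **OS.** Part 2 status is assigned by poor outcome. If non-response or progression raises the hazard of death, the Part 2 term absorbs that rise, and no adjustment for response or progression is planned.
- **EFS.** One of the two routes into Part 2 is itself an EFS event. The covariate then switches on only once the patient has left the risk set.

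At stake is a prespecified hazard ratio that could be read as showing that pacritinib plus HMA shortens survival when the added HMA does nothing.

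**Working it through.** The plan gives no effect size, event count or power for EFS or OS, so there is no stated figure to reproduce. I compared the definitions and then sized the two effects.

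**EFS: who is still at risk on entering Part 2?** From the documents: ORR 15% (the Part 1 target), N = 40, and 4 cycles of 28 days (112 days, about 3.7 months). Assumed: monthly progression hazard *h* in non-responders, half that in responders (counted to 12 months), full uptake, and no deaths before entry.

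- Entry by progression: 40 × [0.85(1 − e^(−3.7h)) + 0.15(1 − e^(−6h))]
- Entry with stable disease: 40 × 0.85 e^(−3.7h)

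At *h* = 0.03 the first is 40 × (0.0893 + 0.0247) = 4.6 and the second is 40 × 0.761 = 30.4.

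| Monthly *h* | By progression | With stable disease | Share by progression |
|---|---|---|---|
| 1% | 2 | 33 | 5% |
| 3% | 5 | 30 | 13% |
| 6% | 9 | 27 | 24% |
| 10% | 13 | 23 | 36% |

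Entrants by progression add no exposed time at risk. Stable-disease entrants do, so the term can be estimated, but it compares non-responders on the combination mainly with responders and with everyone's first 4 cycles.

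**OS: what does the coefficient estimate when HMA is inert?** Let poor outcome multiply the death hazard by *k*, and let a fraction *u* of eligible patients enter Part 2. Just after cycle 4, ignoring earlier progression, the unexposed are responders (weight 0.15, hazard 1) and non-takers (weight 0.85(1 − *u*), hazard *k*). The exposed have hazard *k*. So

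HR ≈ *k* ÷ {[0.15 + 0.85(1 − *u*)*k*] ÷ [0.15 + 0.85(1 − *u*)]}.

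With *u* = 1 this is simply *k*. With *u* = 0.9 and *k* = 2 it is 2 ÷ (0.32 ÷ 0.235) = 1.47. For *k* = 1.5 and 3 it gives 1.27 and 1.74.

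Simulated large-sample Cox fits with a start-stop Part 2 indicator and a true HMA hazard ratio of 1.0 agree:

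- **Set A** (baseline median OS 60 months, 3% monthly progression, hazard rising at non-response or progression, 36 months of follow-up, 90% uptake): 1.18, 1.51 and 1.80 for *k* = 1.5, 2 and 3. A larger repeat gave 1.23, 1.45 and 1.83. With full uptake it gave 1.48, 1.92 and 3.03.
- **Set B** (monthly hazards 0.02 for death and 0.06 for progression, responders' hazards halved, hazard rising at progression only, 24 months of follow-up, full uptake): about 2.1 to 2.6 for *k* = 2 and 3.2 to 3.6 for *k* = 3. With 90% uptake: 1.7 to 2.0 and 1.9 to 2.8.

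**Precision at N = 40** (set A, 90% uptake). The 10th to 90th percentile of the estimate is 0.45 to 3.1 with no confounding (about 14 deaths) and 0.69 to 3.65 at *k* = 2 (about 21 deaths).

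**Does adjustment help?** I added time-dependent response and progression as main effects at 90% uptake. The Part 2 hazard ratio became 0.98 to 1.03 in set B but stayed at 1.08 to 1.32 in set A, where the hazard rises only once and main effects do not match the mechanism. At 90% uptake the comparison of like with like rests on about 0.1 × 35 = 3.5 patients. At full uptake it cannot be made.

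**The case against.** The strongest defence is that the sentence shows sound instinct. Time-dependent covariates point naturally to an extended Cox model, which can sit beside Kaplan-Meier estimates and log-rank tests. Coding Part 2 this way avoids immortal-time bias. The plan never says the coefficient will be read as the effect of HMA; it may be meant only as adjustment for a treatment change. EFS and OS are not primary, are not among the secondary endpoints listed in Section 10.0, and drive no stopping rule. All of this stands. It limits the stakes but does not supply the missing model or make the coefficient interpretable.

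A reader might infer more than the documents support:

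- **That entering Part 2 is itself the EFS event.** This is true only for entry by progression. Table 9 keeps stable disease apart from failure. Section 12.0 does use the word failures for early dropouts, but only in the ORR analysis.
- **That the analysis cannot be run.** It can; the model is simply unnamed.
- **That the term distorts the planned subgroup comparisons.** Those are log-rank tests and carry no Part 2 term.
- **That a hazard ratio of 2 to 3.5 is to be expected.** Set B implies a median OS of about 22 to 27 months. Section 2.1 gives 5.7 years for Low and 3.5 years (42 months) for Int-1 disease.

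**Conclusion.** The concern holds in this form: the model is unspecified, and the Part 2 coefficient would not be a treatment effect for either endpoint.

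For OS the direction is robust under the assumptions examined: whenever non-response or progression raises the death hazard, an inert HMA looks harmful. The size is not robust. Roughly 1.2 to 3.6 covers multipliers of 1.5 to 3 and uptake of 90% or 100%, and none of those inputs comes from the documents. Set A with *k* = 1.5 gives a median OS of about 42 months, matching the Int-1 figure in Section 2.1, and a hazard ratio of about 1.2 at 90% uptake or 1.5 at full uptake. With at most 40 patients, sampling error is as large a problem as the bias.

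For EFS the term is uninformative for entrants by progression and conditional on non-response for the rest. The primary ORR analysis is untouched. The change is worth making because it is cheap.

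**What to change.** Replace the sentence with the following.

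- **EFS** runs from the first pacritinib dose to first progression or death from any cause, per Table 9, with a stated censoring rule and no Part 2 term.
- **OS** runs from the first dose for all patients, by Kaplan-Meier. Comparisons between baseline subgroups carry no Part 2 term. Any exploratory Cox model with a start-stop Part 2 indicator also includes time-dependent response and progression status. Its Part 2 coefficient is not reported as the effect of adding HMA, because adjustment may remove only part of the bias.
- **Part 2** EFS and OS are reported descriptively from the first day of combination therapy, with progression judged against a new baseline at Part 2 entry. Without that baseline, patients who entered by progression would have no usable EFS.

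The cost is SAP wording and a little programming, with no change to design, enrolment or treatment. The trial gives up any claim about the survival effect of adding HMA, which this design cannot support.

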12.0 PROTOCOL ADMINISTRATION

Protocol specific data will be entered into PDMS/CORe.

Protocol amendments

Changes to the protocol will be made only when protocol amendments have been signed by the principal investigator and approved by the ethical committee of MD Anderson Cancer Center.

Archival of data

All patient data (including source data) generated in connection with this study will be kept in the archives of the MDACC in accordance with 21 CFR 312.62. All data will be available for inspection by company representatives of the Medical Department and by regulatory authorities.

13.0 REPORTING REQUIREMENTS

The Investigator or physician designee is responsible for verifying and providing source documentation for all adverse events and assigning the attribution for each event for all subjects enrolled on the trial. The PI or designee will be responsible for determining attribution for all events.

Grade 3 or 4 related and/or unexpected adverse events and protocol specific data will be entered into PDMS/CORE. PDMS/CORE will be used as the electronic case report form for this protocol.

Reporting Requirements

The descriptions and grading scales found in the revised NCI Common Terminology Criteria for Adverse Events (CTCAE) version 4.0 will be utilized for adverse event reporting. (<http://ctep.cancer.gov/reporting/ctc.html>).

Adverse event reporting will be as per the NCI criteria and the MDACC Leukemia Specific Adverse Event Recording and Reporting Guidelines.

Adverse event is any untoward medical occurrence that may present during treatment with a pharmaceutical product but which does not necessarily have a causal relationship with this treatment.

Adverse drug reaction is a response to a drug which is noxious and unintended and which occurs at doses normally used in man for prophylaxis, diagnosis, or therapy of disease or for the modification of physiologic function.

Assessing causal connections between agents and disease is fundamental to the understanding of adverse drug reactions. In general, a drug may be considered a contributory cause of an adverse event if, had the drug not been administered, 1) the event would not have happened at all, 2) the event would have occurred later than it actually did, or 3) the event would have been less severe.

Adverse Events (AEs) will be evaluated according to the most current version of the Pacritnib Investigator Brochure for expectedness. The current CTC version will be used to assess and grade AE severity. Only unexpected AEs will be recorded in the Case Report Form (CRF). Expected events during leukemia therapy are:

1. *Myelosuppression related events (due to disease or leukemia therapy)*
 - a. *febrile or infection episodes not requiring management in the intensive care unit*
 - b. *epistaxis or bleeding except for catastrophic CNS or pulmonary hemorrhage*
 - c. *anemia, neutropenia, lymphopenia, thrombocytopenia, leukopenia, leukocytosis*
2. *Disease related events*
 - a. *symptoms associated with anemia*
 - i. *fatigue*
 - ii. *weakness*

- iii. *shortness of breath*
 - b. *electrolyte abnormalities (sodium, potassium, bicarbonate, CO₂, magnesium)*
 - c. *chemistry abnormalities (LDH, phosphorus, calcium, BUN, protein, albumin, uric acid, alkaline phosphatase, glucose)*
 - d. *coagulation abnormalities*
 - e. *disease specific therapy (induction, maintenance, salvage, or stem cell therapy)*
 - f. *alopecia*
 - g. *bone, joint, or muscle pain*
 - h. *liver function test abnormalities associated with infection or disease progression*
 - i. *disease progression*
- 3. *General therapy related events*
 - a. *catheter related events*
 - b. *renal failure related to tumor lysis syndrome or antibiotic/antifungal therapy*
 - c. *rash related to antibiotic use*
- 4. *Hospitalization for the management of any of the above expected events*

Abnormal hematologic values will not be recorded on the CRF. For abnormal chemical values grade 3 or 4, the apogee will be reported per course in the CRF.

Serious Adverse Event Reporting (SAE)

An adverse event or suspected adverse reaction is considered “serious” if, in the view of either the investigator or the sponsor, it results in any of the following outcomes:

- Death
- A life-threatening adverse drug experience – any adverse experience that places the patient, in the view of the initial reporter, at immediate risk of death from the adverse experience as it occurred. It does not include an adverse experience that, had it occurred in a more severe form, might have caused death.
- Inpatient hospitalization or prolongation of existing hospitalization
- A persistent or significant incapacity or substantial disruption of the ability to conduct normal life functions.
- A congenital anomaly/birth defect.

Important medical events that may not result in death, be life threatening, or require hospitalization may be considered a serious adverse drug experience when, based upon appropriate medical judgment, they may jeopardize the patient or subject and may require medical or surgical intervention to prevent one of the outcomes listed in this definition. Examples of such medical events include allergic bronchospasm requiring intensive treatment in an emergency room or at home, blood dyscrasias or convulsions that do not result in inpatient hospitalization, or the development of drug dependency or drug abuse (21 CFR 312.32).

- Important medical events as defined above, may also be considered serious adverse events. Any important medical event can and should be reported as an SAE if deemed appropriate by the Principal Investigator or the IND Sponsor, IND Office.
- All events occurring during the conduct of a protocol and meeting the definition of a SAE must be reported to the IRB in accordance with the timeframes and procedures outlined in the University of Texas M. D. Anderson Cancer Center Institutional Review Board Policy

for Investigators on Reporting Unanticipated Adverse Events for Drugs and Devices. Unless stated otherwise in the protocol, all SAEs, expected or unexpected, must be reported to the IND Office, regardless of attribution (within 5 working days of knowledge of the event).

- All life-threatening or fatal events, that are unexpected, and related to the study drug, must have a written report submitted within 24 hours (next working day) of knowledge of the event to the Safety Project Manager in the IND Office.
- Unless otherwise noted, the electronic SAE application (eSAE) will be utilized for safety reporting to the IND Office and MDACC IRB.
- Serious adverse events will be captured from the time of the first protocol-specific intervention, until 30 days after the last study treatment/intervention, unless the participant withdraws consent. Serious adverse events must be followed until clinical recovery is complete and laboratory tests have returned to baseline, progression of the event has stabilized, or there has been acceptable resolution of the event.
- Additionally, any serious adverse events that occur after the 30 day time period that are related to the study treatment must be reported to the IND Office. This may include the development of a secondary malignancy.
 - Serious adverse events will be forwarded to FDA by the IND Sponsor (Safety Project Manager IND Office) according to 21 CFR 312.32.

It is the responsibility of the PI and the research team to ensure serious adverse events are reported according to the Code of Federal Regulations, Good Clinical Practices, the protocol guidelines, the sponsor's guidelines, and Institutional Review Board policy.

Reporting of external SAEs

- The MDACC institutional policy for reporting of external SAEs will be followed.

It is the responsibility of the PI and the research team to ensure serious adverse events are reported according to the Code of Federal Regulations, Good Clinical Practices, the protocol guidelines, the sponsor's guidelines, and Institutional Review Board policy.

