The monitoring rule for the toxicity rate, based on these assumptions and monitoring conditions above is found in Table 11. For example, accrual will cease if 4 or more patients experience toxicities among the first 5 patients.

Table 11. Stop accrual if the number of drug-related non-hematological grade 3/4 toxicities is greater than or equal to indicated (i.e., # patients with toxicities) among the number of patients evaluated								
# patients evaluated	5	10	15	20	25	30	35	40
# patients with toxicities	4-5	5-10	6-15	7-20	8-25	10-30	11-35	Always stop with this many patients

Monitoring the ORR rate, based on the above assumptions and monitoring conditions is found in Table 12. For example, accrual will cease if 0 patients experience an overall response within 4 cycles in the first 15 patients treated.

Table 12. Stop accrual if the number with overall response is less than or equal to indicated (i.e., # patients with overall response) among the number of patients evaluated					
# patients evaluated	5-10		15-25	30-35	40
# patients with overall response	Never Stop with this many patients		0	0-1	Always stop with this many patients

Multc Lean Desktop (version 2.1.0) was used to generate the toxicity and futility stopping boundaries and the OC table (Table 13). In order to utilize the software for the design, a response constant rate of 0.15 and beta (0.3, 1.7) priors were assumed for the standard treatment response distribution and experimental treatment response prior distribution, respectively. In addition, a 15% toxicity constant rate and beta (0.3, 1.7) priors were assumed for the standard treatment toxicity constant rate and experimental treatment toxicity prior distribution, respectively.

The probability of stopping the study early if the true ORR of the Pacritinib was 15% and the true toxicity rate was 15% was 21.9%. Probabilities of stopping early for high true toxicity rates (i.e., 40%) were 95.3% when the true ORR was 15%, and 94.4% when true ORR rate was 30%.

Table 13. Operating characteristics for simultaneous monitoring response and toxicity rates for patients treated with Pacritinib treatment

True Toxicity Rate	True ORR	Prob(stop the trial early)
0.05	0.05	0.6908
	0.10	0.3528
	0.15	0.1654
	0.20	0.0754
	0.25	0.0338
	0.30	0.0150
0.10	0.05	0.6944
	0.10	0.3603
	0.15	0.1750
	0.20	0.0861
	0.25	0.0450
	0.30	0.0264
0.15	0.05	0.7109
	0.10	0.3947
	0.15	0.2194
	0.20	0.1352
	0.25	0.0964
	0.30	0.0787
0.20	0.05	0.7533
	0.10	0.4836
	0.15	0.3341

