	0.20	0.2623
	0.25	0.2292
	0.30	0.2141
0.30	0.05	0.8956
	0.10	0.7815
	0.15	0.7182
	0.20	0.6879
	0.25	0.6378
	0.30	0.6675
0.40	0.05	0.9826
	0.10	0.9635
	0.15	0.9529
	0.20	0.9478
	0.25	0.9455
	0.30	0.9444
0.50	0.05	0.9990
	0.10	0.9979
	0.15	0.9973
	0.20	0.9970
	0.25	0.9969
	0.30	0.9968

Study design: Part 2

The standard practice is to put these patients on observation, an ORR rate of about 30% is

clinically relevant. The target ORR with the experimental treatment is 30%. The regimen of the Pacritinib + HMA will be considered worthy of further investigation if it elicits an increase in ORR to 30% with acceptable toxicity. A >30% therapy related non-hematological grade 3/4 toxicity rate is considered unacceptable. Thus, interim monitoring rules, assuming the prior distributions below, were constructed that meet the following two conditions,

- 1) Stop if $\text{Prob}\{p(\text{ORR}, E) < 0.30 \mid \text{data}\} > 0.975$, or
- 2) Stop if $\text{Prob}\{p(\text{TOX}, E) > 0.30 \mid \text{data}\} > 0.95$,

where $P(\text{ORR}, E)$ and $P(\text{TOX}, E)$ are the true ORR and toxicity rates for the Pacritinib + HMA, and $p(\text{ORR}, H)$ is the true ORR rate of the standard treatment. The first rule provides for stopping the study if the data suggest that it is unlikely (i.e., probability < 2.5%) that ORR rate of the Pacritinib + HMA treatment is greater than 30.0%. The second condition will stop the study early if excessive therapy-related non-hematological grade 3/4 toxicity (>30.0%) is highly probable (i.e., probability >95.0%) for the Pacritinib + HMA. Monitoring for toxicity and futility will not begin until 5 patients have been evaluated, and cohort size for future evaluations is 5. The monitoring rule for the toxicity rate, based on these assumptions and monitoring conditions above is found in Table 14. For example, accrual will cease if 4 or more patients experience toxicities among the first 5 patients.

Table 14. Stop accrual if the number of drug-related non-hematological grade 3/4 toxicities is greater than or equal to indicated (i.e., # patients with toxicities) among the number of patients evaluated								
# patients evaluated	5	10	15	20	25	30	35	40
# patients with toxicities	4-5	6-10	8-15	10-20	12-25	14-30	16-35	Always stop with this many patients

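### Section 13.0 gives two conflicting rules for entering expected, drug-related grade 3/4 non-hematological adverse events in the eCRF, and the toxicity stopping rules count those events

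*Combined protocol and SAP*

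**What the plan says.** Section 13.0 (Reporting Requirements) states: "Grade 3 or 4 related and/or unexpected adverse events and protocol specific data will be entered into PDMS/CORE". It then names that system as the trial's electronic case report form. Later the section refers expectedness to the current Investigator Brochure and states: "Only unexpected AEs will be recorded in the Case Report Form (CRF". A printed list of expected events follows directly. Besides blood counts it includes fever or infection managed outside intensive care, bleeding short of catastrophic CNS or pulmonary hemorrhage, fatigue and weakness linked to anemia, alopecia, and bone, joint or muscle pain.

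Two laboratory rules come after the list: "Abnormal hematologic values will not be recorded on the CRF" and "For abnormal chemical values grade 3 or 4, the apogee will be reported per course in the CRF". Section 12.0 (Protocol Administration) adds "Protocol specific data will be entered into PDMS/CORe" but does not define the term.

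These data have two uses in Section 12.0 (Statistical Considerations). The Part 1 safety rule is headed "Table 11. Stop accrual if the number of drug-related non-hematological grade 3/4 toxicities is greater than or equal to indicated", and Table 14 applies the same event definition in Part 2. Neither mentions expectedness. The analysis plan says "Toxicity type, severity and attribution will be summarized for each patient using frequency tables" and sets no lower limit on grade.

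**The concern.** Both entry sentences govern the same instrument, and they disagree on the class of event that drives the toxicity stopping rules. A data manager following the first sentence enters an expected, drug-related grade 3 event. One following the second does not.

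If the second were followed and the interim counts came from the eCRF, the observed toxicity count would fall below the true one. The rules would then stop an unacceptably toxic regimen less often than designed. Safety and tolerability are part of the trial's only stated objective, and Part 2 adds a hypomethylating agent to pacritinib, so the input to these rules should not depend on which sentence a site follows.

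**Working it through.** **1. The two sentences side by side**

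The first sentence can be parsed with the grade restriction on related events only, or on related and unexpected events alike. The first two rows below are the same under either parse.

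| Non-hematological clinical event, drug-related | First sentence | Second sentence | Counted in Tables 11 and 14 |
|---|---|---|---|
| Grade 3/4, expected | enter | do not enter | yes |
| Grade 1-2, expected | not required | do not enter | no |
| Grade 3/4, unexpected | enter | enter | yes |

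The first row is the conflict. The second row is a gap, not a conflict.

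**2. Does the first row contain anything without the brochure?**

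Yes. The heading over the infection and bleeding items covers effects of therapy as well as of disease, so a drug-related grade 3 infection treated on a general ward is expected under the printed list. The fatigue and bone, joint or muscle pain items sit under disease-related events. They apply less clearly once an event is attributed to the drug, but staff could still code them as expected. This takes non-hematological to mean anything other than a blood-count abnormality, since the plan does not define the term.

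**3. The plan's own boundaries, reproduced**

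Part 1 inputs (Section 12.0): prior beta(0.3, 1.7), limit 0.15, cut-off 0.975, looks every 5 patients. The boundary is the smallest x with P(Beta(0.3+x, 1.7+n−x) > 0.15) > 0.975. For n = 5, 10, ..., 35 this gives 4, 5, 6, 7, 8, 10, 11, matching Table 11.

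Part 2 inputs: prior beta(0.6, 1.4), limit 0.30, cut-off 0.95. The result is 4, 6, 8, 10, 12, 14, 16, matching Table 14. The Table 16 entry for 50% toxicity and 30% response also reproduces (0.8484).

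The Table 13 entries checked do not reproduce from the printed boundaries. At 15% toxicity and 15% response, for example, the table gives 0.2194 and the calculation gives 0.1471. That is a separate matter. The Part 1 figures below therefore come from the Table 11 boundary directly.

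**4. What under-entry would do**

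Let p be the true rate of patients with a qualifying toxicity and c the share of those patients who are entered. The rule then sees a rate of c × p. Early-stop probabilities follow by exact binomial recursion over the looks at 5 to 35 patients. The documents do not give c, so its values are assumptions. For Part 2, toxicity and response are treated as independent.

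| c (assumed) | Part 1, toxicity rule alone, p = 30% | Part 1, toxicity rule alone, p = 40% | Part 2, both rules, p = 50%, ORR 30% |
|---|---|---|---|
| 1.00 | 0.61 | 0.93 | 0.85 |
| 0.75 | 0.26 | 0.61 | 0.41 |
| 0.50 | 0.04 | 0.16 | 0.13 |
| 0.25 | 0.001 | 0.006 | 0.09 |

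In Part 2 the futility rule alone gives about 0.08, so the last column cannot fall below that. The table applies only if the second sentence governs and counts are taken from the eCRF.

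**The case against.** The strongest reply is that the sentences can be reconciled. Chemistry abnormalities are on the expected list, yet their grade 3/4 peaks go in the CRF. The unexpected-only rule is therefore not literally exclusive, and the first sentence can be read as another exception, for related grade 3/4 events. On that reading every stopping-rule input is entered. This is a fair reading and probably the intended one. The protocol does not state it, however, and the laboratory exception does not reach clinical events.

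Second, no document says that monitoring or the toxicity tables use the eCRF alone. Section 13.0 requires source documentation and attribution for all adverse events, Section 8.0 requires assessment at each clinic visit, and all serious events go to the IND Office whether expected or not. The institutional recording guideline, cited without its content, may also ask for more. All of this stands. It rules out a claim that data are lost, but it does not settle which sentence governs the eCRF.

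Third, a reader might infer that most of the drug's low-grade toxicity would go unrecorded. Section 2.3 gives 139 patients with diarrhea, 15 of them at grade 3/4, so 124/139 = 89% had no reported grade 3/4 diarrhea. That figure measures a gap only if the brochure lists gastrointestinal events as expected. The brochure's tables are not in the documents, and the printed list names neither diarrhea nor nausea, so a site using that list alone would enter both. One symptom also does not stand for all low-grade toxicity.

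Fourth, a reader might set the earlier 33/191 = 17.3% of patients with grade 3/4 gastrointestinal events against the 15% Part 1 limit. The first figure is all-cause and gastrointestinal only. The limit concerns drug-related events of every non-hematological type. The first neither bounds nor estimates the second.

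**Conclusion.** The inconsistency is real and minor. Read literally, Section 13.0 both requires and excludes eCRF entry of expected, drug-related grade 3/4 non-hematological events, which Tables 11 and 14 count. This does not depend on the brochure, because the printed list already supplies such events.

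The effect on stopping could be large, as the table shows, but it rests on three things the documents do not establish: that staff follow the second sentence, that monitoring draws on the eCRF, and the value of c. A conclusion that the stopping rules will fail is not supported.

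A secondary point is conditional. Neither sentence requires entry of expected, drug-related grade 1-2 events, so the severity tables would be incomplete for them if built from the eCRF alone. Such events can change the dose (Section 5.0), but how much low-grade data to enter is a choice on which reasonable teams differ.

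**What to change.** In Section 13.0, delete the sentence "Only unexpected AEs will be recorded in the Case Report Form (CRF" and replace the first entry sentence with:

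> All drug-related grade 3 or 4 non-hematological AEs, expected or not, all unexpected AEs, and any AE leading to a dose hold, reduction or discontinuation will be entered in PDMS/CORE with grade and attribution, together with protocol specific data. The toxicity monitoring in Tables 11 and 14 uses these entries.

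Add to the two laboratory rules that they do not apply to an abnormality that must itself be entered as an adverse event under this text. Otherwise a dose hold for low platelets would clash with "Abnormal hematologic values will not be recorded on the CRF".

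Entry of all expected, drug-related grade 1-2 events is optional. If the team leaves them out, the analysis plan should say that the severity tables do not cover them, or that they will be taken from source.

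The cost is slightly more data entry in at most 40 patients. Assessment at each visit, source documentation and attribution are already required, so no new visit or test is needed.
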